11.2.2 Planned recruitment rate

The estimate recruitment period for the trial is 15 months.

11.3 Randomisation methods

A random sequence for study arm allocation will be computer generated by a randomisation service provider (SealedEnvelope.com). Sealed Envelope will provide a unique trial identification code for each recruited participant. Stratified randomisation will be performed with strata defined by MSA sub-type. Blocking will be used within strata to enable achievement of equal numbers in each group.

Strata 1 = MSA of parkinsonian sub-type (MSA-P)

Strata 2 = MSA of cerebellar sub-type (MSA-C)

At the baseline visit, the clinical investigator will enter the patient's initials, gender, date of birth, date of consent, criteria fulfilment and MSA sub-type strata into the SealedEnvelope.com secure website which will then allocate the appropriate trial identification code to the patient.

11.4 Statistical analysis plan

11.4.1 *Summary of baseline data and flow of participants*

A CONSORT diagram will be used to describe the course of patients through the trial. Baseline characteristics will be summarised by randomised group. Summary measures for the baseline characteristics of each group will be presented as mean and standard deviation for continuous (approximate) normally distributed variables, medians and interquartile ranges for non-normally distributed variables, and frequencies and percentages for categorical variables. The impact of missing data and non-compliance will be investigated.

11.4.2 *Primary outcome analysis*

The primary outcome will be the difference in total Unified Multiple System Atrophy Rating Scale (UMSARS) score (Parts I and II) at 48 weeks. The primary analysis will compare exenatide patients to be best medically treated patients using a regression (ANCOVA) model that adjusts for baseline severity and MSA subtype. All modelling assumptions will be checked. The statistical analysis will be based on all participants as randomised, irrespective of subsequent compliance with allocated treatment (intention to treat analysis). The impact of missing data and non-compliance will be investigated as appropriate.

11.4.3 *Secondary outcome analysis*

Key secondary outcomes would include loss of independent ambulation by end of study, defined by a score of 4 or more in UMSARS-I item 7 (walking); MSA-QoL scale UMSARS parts I, II, III and IV at week 48 and 96; use of anti-parkinsonian or anti-orthostatic hypotension drugs; number of falls; and the proportion of patients reaching a score of 3 or more on UMSARS-I items 1 (speech), 2 (swallowing), and 8 (falling); clinical global impression (CGI) at week 48 and 96; MoCA scores at week 48 and 96. These outcomes will be analysed using appropriate statistical methods, adjusting for baseline values where possible. Again, all assumptions will be checked.

11.4.4 *Sensitivity and other planned analyses*

Sensitivity analyses will be performed to identify differences between patients who drop-out or have missing data and patients with complete data for each variable.

11.5 Other statistical considerations

Any deviation(s) from the original statistical plan will be described and justified in the final report.

12 Record keeping and archiving

At the end of the trial, all essential documentation will be archived securely by the CI and trial sites for a minimum of 25 years from the declaration of end of trial.

Essential documents are those which enable both the conduct of the trial and the quality of the data produced to be evaluated and show whether the site complied with the principles of Good Clinical Practice and all applicable regulatory requirements.

The sponsor will notify sites when trial documentation can be archived. All archived documents must continue to be available for inspection by appropriate authorities upon request.

13 Oversight Committees

13.1 Trial Management Group (TMG)

The TMG will include the Chief Investigator and trial staff. The TMG will be responsible for overseeing the trial. The group will meet to discuss trial progress every 3 months as stated in the TMG terms of reference.

The TMG will review recruitment figures, SAEs and substantial amendments to the protocol prior to submission to the REC and/or MHRA.

13.2 Trial Steering Committee (TSC)

The role of the TSC is to provide overall supervision of the trial. The TSC will review the recommendations of the Data Monitoring Committee and, on consideration of this information, recommend any appropriate amendments/actions for the trial as necessary. The TSC acts on behalf of the funder(s) and Sponsor.

13.3 Data Monitoring Committee (DMC)

The role of the DMC is to provide advice on data and safety aspects of the trial but where all members are independent. The membership, frequency of meetings, activity (including review of trial conduct and data) and authority will be covered in the DMC terms of reference. The IDMC will consider data in accordance with the statistical analysis plan and will advise the TSC through its Chair.

14 Direct Access to Source Data/Documents

The investigator(s)/ institution(s) will permit trial-related monitoring, audits, REC review, and regulatory inspection(s), providing direct access to source data/documents. Trial participants are informed of this during the informed consent discussion. Participants will consent to provide access to their electronic health records and medical notes.

15 Ethics and regulatory requirements

The sponsor will ensure that the trial protocol, participant information sheet, consent form, GP letter and submitted supporting documents have been approved by the appropriate regulatory body (MHRA in UK) and an appropriate research ethics committee, prior to any participant recruitment. The protocol, all other supporting documents including and agreed amendments, will be documented and submitted for ethical and regulatory approval as required. Amendments will not be implemented prior to receipt of the required approval(s).

Before the site may be opened to recruit participants, the Chief Investigator or designee must have HRA approval and capacity and capability confirmed in writing from their Trust Research & Development (R&D). It is the responsibility of the CI/ PI or designee at each site to ensure that all subsequent amendments gain the necessary approvals, including HRA approvals (where required) at the site. It is the responsibility of the CI or designee at each site to ensure that all subsequent amendments gain the necessary approvals, including NHS Permission (where required) at the site. This does not affect the individual clinician's responsibility to take immediate action if thought necessary to protect the health and interest of individual participants (see section 9.9 for reporting urgent safety measures).

An annual progress report (APR) will be submitted to the REC within 30 days of the anniversary date on which the favourable opinion was given, and annually until the trial is declared ended. The chief investigator will prepare the APR.

Within 90 days after the end of the trial, the CI/Sponsor will ensure that the main REC and the MHRA are notified that the trial has finished. If the trial is terminated prematurely, those reports will be made within 15 days after the end of the trial.

The CI will supply the Sponsor with a report of the clinical trial which complies with the format as defined by the EMA. This will then be uploaded to EudraCT for availability to the MHRA and a copy of the report will be submitted to the main REC, within 1 year after the end of the trial.

16 Monitoring requirement for the trial

The sponsor will determine the appropriate level and nature of monitoring required for the trial. Risk will be assessed on an ongoing basis and adjustments made accordingly. The degree of monitoring will be proportionate to the objective, purpose, phase, design, size, complexity, blinding, endpoints and risks associated with the trial. A trial specific oversight and monitoring plan will be established for studies. The trial will be monitored in accordance with the agreed plan.

17 Finance

The trial is being funded by the John Black Charitable Foundation and the Van Andel Research Institute. It also has financial support from the Defeat MSA Alliance from the USA. The trial will benefit from support for recruitment via the MSA Trust in the UK.

18 Insurance

University College London holds insurance against claims from participants for injury caused by their participation in the clinical trial. Participants may be able to claim compensation if they can prove that UCL has been negligent. However, as this clinical trial is being carried out in a hospital, the hospital continues to have a duty of care to the participant of the clinical trial. University College London does not accept liability for any breach in the hospital's duty of care, or any negligence on the part of hospital employees. This applies whether the hospital is an NHS Trust or otherwise.

Participants may also be able to claim compensation for injury caused by participation in this clinical trial without the need to prove negligence on the part of University College London or another party. Participants who sustain injury and wish to make a claim for compensation should do so in writing in the first instance to the Chief Investigator, who will pass the claim to the Sponsor's Insurers, via the Sponsor's office.

Wenning, Gregor K, Felix Geser, Florian Krismer, Klaus Seppi, Susanne Duerr, Sylvia Boesch, Martin Köllensperger, et al. 2013. "The Natural History of Multiple System Atrophy: A Prospective European Cohort Study." *The Lancet Neurology* 12 (3): 264–74.

Screening (Pre-treatment assessment)		Treatment Phase					Final visit	
Visit No:	1	2	Telephone call	3	4	5	6	Telephone call
Day – 28 to Day -1	Day 0	Week 4 ⁶	Week 12	Week 24	Week 36	Week 48 / Discontinuation visit	Week 58 ⁷	Week 96
Window of flexibility for timing of visits:		+/- 7 days	+/- 7 days	+/- 7 days	+/- 7 days	+/- 7 days	+/- 7 days	+/- 7 days
Informed Consent	X							
Demographics	X							
Medical History ¹	X							
Height	X							
Weight	X	X	X	X	X	X	X	X
Physical Examination	X	X*	X*	X*	X*	X*	X*	X*
Neurological Examination	X	X*	X*	X*	X*	X*	X*	X*
Vital Signs ²	X	X	X	X	X	X	X	X
12-Lead ECG	X							
Routine blood test ³	X		X	X	X	X	X	
Fasting blood tests ⁴		X		X	X	X	X	
Lumbar puncture + 10ml serum sample		X					X	X ¹⁰
MoCA	X	X	X	X	X	X	X	X
BDI-II	X	X	X	X	X	X	X	X

UMSARS Part 1, 3 and 4	X	X	X	X	X	X	X
UMSARS Part 2 (videotaped)	X	X	X	X	X	X	X
COMPASS Select	X			X		X	X
COMPASS Change				X		X	X
MSA-QoL scale	X				X		X
Timed Motor Tests	X		X	X	X	X	X
The Unified Dystonia Rating	X		X	X	X	X	X
Eligibility confirmation	X	X					
Randomisation		X ⁸					
IMP administration ⁵	X		X	X	X		
Adverse Events/SAEs review	X	X	X	X	X	X	X
Concomitant Medication review	X	X	X	X	X	X	X

Appendix 1 - Schedule of assessments

1. Medical History: including MSA history, family history, medication history, previous imaging, previous genetic tests and previous drug compliance issues.
2. Vital signs: blood pressure, respiratory rate, heart rate, temperature, oxygen saturation and weight.
3. Routine blood tests: FBC, U&E, LFT, glucose, amylase, HbA1c, PT and APTT (PT and APTT not done at weeks 24 and 36).
4. Fasting blood tests
 - Baseline visit: glucose, insulin, c-peptide, and triglycerides.
 - Week 24 visit: glucose, insulin, c-peptide.
 - Week 48 visit: glucose, insulin, c-peptide.
5. 5 IMP administration: Participants will be randomly allocated into 2 groups to receive either Exenatide (n[~]=25) or best medical treatment (n[~]=25). Only participants randomised to the Exenatide arm will receive the IMP.
 6. At Week 4 the study nurse will call the participants to provide support and optimise compliance.
 7. At Week 58 the study nurse will call the participants to perform an adverse event check.

8. Randomisation will occur once eligibility has been confirmed prior to Visit 2 to allow Pharmacy team time to prepare IMP for dispensing.
9. * Clinical and Neurological examinations will be performed with deemed relevant/necessary by trial clinician for clinical purposes.
10. Only a serum sample will be collected for research purposes at week 96.

Appendix 2

COVID19 mitigation plans

The objective of this Appendix is to set out a plan detailing the proposed continuation of the Exenatide-MSA trial if a restriction in trial Face to Face visits should occur as a result of a resurgence of COVID19 infections.

CONTINUATION OF IMP DISPENSING FOR EXISTING TRIAL RECRUITS

1. Patient consent required. Each patient will be contacted by the research team, at site. Consent to ship IMP to the patients home to be fully documented in source notes
2. Patient will be assessed via telephone by Chief Investigator (or appropriate delegated trial team member) to decipher whether suitable to dispense IMP. Specific questions to be asked in relation to abdominal pain/ weight/ AEs/ new con-meds etc.
3. NB Scheduled blood tests will not be performed. Given that Exenatide is licensed for the treatment of Type 2 Diabetes that does not routinely require regular monitoring of patient safety using blood tests, these will not be performed unless a patient describes symptoms potentially indicating an adverse effect of the IMP. In the event of a clinically significant adverse reaction to the IMP, dispensing will be paused until a face to face evaluation of the participant can be completed.
4. If a patient describes adverse events that require urgent medical treatment, appropriate clinical advice will be given to patient regarding all/ any necessary precautions/ investigations/ treatment options through trial team/ GP/ local hospital facilities.

If it is deemed suitable to dispense IMP:

- A) Consent for telephone follow-up and IMP delivery obtained verbally and documented (as per MHRA/ HRA advice)
- B) IMP prescribed by trial team (as normal)
- C) Courier collects IMP from NHNN Pharmacy
- D) Upon arrival at participants address courier has agreed to unpack the IMP from cooler, wipe them down (alcohol wipe), place at the patients door and ring and then step back (to minimise COVID-19 transmission risk). Patients will be informed by site team when to expect the delivery.
- E) The site team shall then call the patient and confirm and document delivery.

REMOTE ASSESSMENTS

To minimise disruption to the scientific integrity of the trial, for patients who remain well but who are unable to attend a scheduled trial visit due to National guidelines/ patient concerns regarding risk of travel, face to face evaluation will be replaced by remote evaluation. Questionnaires will be completed remotely and a Video examination of UMSARS part 2 will be performed with the exception that Rigidity will not be rated (Item 6), and the Pull test will not be performed (Item 13) . These remote measures will be appropriately labelled to ensure that any necessary adjustments for remote/ face to face assessments are incorporated in the final statistical analysis of the trial.

Visit CRFs will otherwise be completed in full. The fact that this visit has taken place by video/ telephone will be documented on paper CRF and source notes along with all relevant visit information.

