6.5 Concomitant medication

Trial participants will be permitted to use any licensed medication throughout the course of the trial that is recommended by their referring Neurologist and is not contraindicated with trial IMP as per standard practice. Patients will be given advice in any necessary minor adjustments to their pre-existing MSA medications at each of their follow up visits and doses will be recorded and converted to a Levodopa equivalent dose (LED) as appropriate. No routine adjustment of MSA medications will be made by the Investigator(s) unless at the request of the patients. If possible, patients will be invited to attend the trial site at a similar time of day and after a similar duration since they took their usual MSA medications for each of the trial visits.

Patients receiving warfarin or coumarin derivatives may be at risk of increased INR and associated bleeding; therefore INR should be monitored closely at each participant's visit.

Patients on Warfarin will not be able to undergo Lumbar punctures.

There have been rare reported events of altered renal function with Exenatide; therefore patients receiving the following concomitant medications should have their renal function closely monitored using blood tests at every follow up visit:

- angiotensin converting enzyme inhibitors,

- angiotensin-II antagonists,
- non-steroidal anti-inflammatory medicinal products
- diuretics

COVID-19 vaccinations that are administered after a patient has signed informed consent should be captured as a concomitant medication. If the vaccination is a multi-dose vaccination, each dose received should be entered as a separate concomitant medication.

Concomitant medications will be recorded in the participant's notes in the local electronic health record system, EPIC.

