8.4 Subsequent assessments and procedures

Week 4 (+/-1 week) – telephone call

The study nurse will call the participants to ensure the participants are taking their medication according to the protocol requirements and completing their trial diary as required. They will also perform a concomitant medication and AE check.

Week 12 assessments – Visit 3

At 12 weeks after baseline evaluation, each patient will be telephoned 1 week prior to remind them of their visit

Participants will attend the research centre for the following trial procedures:

- Physical Examination (if deemed necessary by trial clinician for clinical purposes)
- Routine blood tests (FBC, U&E, LFT, glucose, amylase, HbA1c, PT and APTT)
- Serum collection
- Vital signs including weight
- UMSARS Part II (videotaped)
- UMSARS Part I, III and IV
- The Unified Dystonia Rating Scale
- MoCA
- Timed Motor tests
- BDI-II
- Concomitant Medications review
- Adverse Events review
- Dispensing of 12 exenatide (Bydureon or Bydureon BCise) pens (if randomised to receive exenatide).

All participants will be invited for face to face visits at all timepoints. If a participant is unable or unwilling to attend any of the follow up assessments (12,24,36,48,96 weeks), they may be offered the option of a home visit by one or more members of the trial clinical team if staffing levels permit. These participants will be asked to consent to home visits. Assessments will be performed as per protocol. Weight will be measured only if the participant is able to stand, and weighing scales are available. Dispensing of IMP will be performed by trial pharmacy and transported to the patient in an appropriate Cool Bag with temperature logger by the clinical trial team.

Week 24 assessments – Visit 4

At 24 weeks after baseline evaluation, each patient will be telephoned 1 week prior to remind them of their visit. They will be asked not to have eaten and to have drunk water only for 6 hours to enable fasting blood samples to be taken.

Participants will attend the research centre for the following trial procedures:

- Physical Examination (if deemed necessary by trial clinician for clinical purposes)
- Neurological Examination (if deemed necessary by trial clinician for clinical purposes)
- Fasting blood tests (FBC, U&E, LFT, glucose, amylase, insulin, c-peptide, HbA1c)
- Serum collection
- Vital signs including weight
- UMSARS Part II (videotaped)

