Short title: Exenatide once-weekly as a treatment for Multiple System Atrophy Sponsor code: 125591

- UMSARS Part I, III and IV
- Timed motor tests
- COMPASS Select
- COMPASS Change
- The Unified Dystonia Rating scale
- BDI-II
- MoCA
- Concomitant Medications review
- Adverse Events review
- Dispensing of 12 exenatide pens (if randomised to receive exenatide).

Week 36 assessments – Visit 5

At 36 weeks after baseline evaluation, each patient will be telephoned 1 week prior to remind them of their visit.

Participants will attend the research centre for the following trial procedures:

- Physical Examination (if deemed necessary by trial clinician for clinical purposes)
- Routine blood tests (FBC, U&E, LFT, glucose, amylase and HbA1c)
- Serum collection
- Vital signs including weight
- UMSARS Part II (videotaped)
- UMSARS Part I, III and IV
- Timed motor tests
- The Unified Dystonia Rating scale
- BDI-II
- MoCA
- Concomitant Medications review
- Adverse Events review
- Dispensing of 12 exenatide (Bydureon or Bydureon BCise) pens (if randomised to receive exenatide).

Week 48 assessments – Visit 6

At 48 weeks after baseline evaluation, each patient will be telephoned 1 week prior to remind them of their visit. They will be asked not to have eaten and to have drunk water only for 6 hours to enable fasting blood samples to be taken.

Participants will attend the research centre for the following trial procedures:

- Physical Examination (if deemed necessary by trial clinician for clinical purposes)
- Neurological Examination (if deemed necessary by trial clinician for clinical purposes)

Short title: Exenatide once-weekly as a treatment for Multiple System Atrophy Sponsor code: 125591

- Fasting blood tests (glucose, insulin and c-peptide)
- Routine blood tests (FBC, U&E, LFT, glucose, amylase, HbA1c, PT and APTT)
- Serum collection
- Lumbar puncture for CSF collection
- Vital signs including weight
- UMSARS Part II (videotaped)
- UMSARS Part I, III and IV
- Timed motor tests
- COMPASS Select
- COMPASS Change
- MSA-QoL scale
- The Unified Dystonia Rating scale
- BDI-II
- MoCA
- Concomitant Medications review
- Adverse Events review
- Axivity lumbar sensor

If a patient cannot attend the clinical research facility and is being assessed via a home visit, no attempt will be made to perform a lumbar puncture and this missed assessment will be recorded as a protocol deviation.

Week 58 (+/-1 week) telephone call

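### Section 6.5 asks for INR at each visit in participants on warfarin or coumarins, but PT is not scheduled at weeks 24 and 36, and Appendix 2 waives scheduled bloods at remote visits without exempting the Section 6.5 groups

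*Protocol*

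**What the plan says.** Section 6.5 of the protocol names two risks with concomitant drugs and attaches a monitoring instruction to each. For warfarin and coumarin derivatives the risk is a raised INR with bleeding, and "therefore INR should be monitored closely at each participant's visit". For ACE inhibitors, angiotensin-II antagonists, NSAIDs and diuretics the risk is altered renal function, and these patients "should have their renal function closely monitored using blood tests at every follow up visit".

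Warfarin users can be enrolled. Sections 7.2 and 7.3 contain no criterion against anticoagulants, and Section 6.5 bars warfarin users only from lumbar puncture.

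The sampling plan is set out in three other places:

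- **Appendix 1, footnote 3** lists PT and APTT in the routine panel and then adds "PT and APTT not done at weeks 24 and 36".
- **Section 8.4** gives the week 24 panel as "Fasting blood tests (FBC, U&E, LFT, glucose, amylase, insulin, c-peptide, HbA1c" and the week 36 panel as "Routine blood tests (FBC, U&E, LFT, glucose, amylase and HbA1c". Neither contains PT. The week 12 and week 48 lists do.
- **Appendix 2, item 3** (the COVID-19 plan) says "Scheduled blood tests will not be performed" unless the patient reports symptoms that might point to an adverse effect of the drug. Its stated reason is that the licensed diabetes use does not call for regular blood monitoring.

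**The concern.** The protocol identifies a hazard, names the safeguard, and then gives a schedule that does not carry it. Staff usually work from the visit lists and the schedule table. Nothing there tells them to add an INR for a participant on warfarin at weeks 24 and 36, and the footnote reads as a flat omission. Appendix 2 goes further. Its reason for waiving bloods rests on the general licensed use, whereas Section 6.5 singles out certain participants because of what they take alongside exenatide.

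At stake is the safety of a small, identifiable group. Two members of staff could each follow a different part of the protocol in good faith and monitor the same participant differently.

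**Working it through.** The plan states no figure to reproduce. The check compares Section 6.5 with the visit lists. I take PT to be the test from which INR is reported, because no visit list and no entry in the Section 8.5 laboratory list names INR separately. The counts rest on the Section 8.4 lists and the Appendix 1 footnotes, because the Appendix 1 grid cannot be read reliably by column in the text available.

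| Follow-up visit | PT listed | U&E listed | Pens dispensed to exenatide arm (8.4) |
|---|---|---|---|
| Week 12 | yes | yes | 12 |
| Week 24 | no | yes | 12 |
| Week 36 | no | yes | 12 |
| Week 48 | yes | yes | none listed |
| Any of these held remotely under Appendix 2 | no, unless symptoms | no, unless symptoms | possible, after telephone assessment |

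**INR instruction, face-to-face schedule.** Follow-up visits up to week 48: 4. Visits with PT: 2 (weeks 12 and 48). Nominal gap between scheduled PT tests: 48 − 12 = 36 weeks. Both visits in that gap dispense further drug.

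**Renal instruction, face-to-face schedule.** U&E is listed at 4 of the 4 follow-up visits up to week 48, so the instruction is met throughout treatment.

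**Both instructions, remote visits.** Appendix 2 item 3 removes all scheduled bloods, and its one exception is symptom-based. Section 6.5 ties monitoring to the visit, whether or not there are symptoms. The telephone assessment asks about new concomitant drugs, so it need not bring up a drug the participant was already taking at entry. Appendix 2 contains no reference to Section 6.5.

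**Visits left out of the count.** Week 96 has research serum only, with neither PT nor U&E, and the baseline list has no PT. Baseline precedes the first dose, and week 96 falls 96 − 48 = 48 weeks after the treatment course. The risks named in Section 6.5 are tied to exenatide, so these two visits add little.

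**The case against.** The best defence is that the two texts have different scopes. Footnote 3 and Section 8.4 define the panel for all participants, and Section 6.5 is an extra instruction for a few. Leaving PT out of the common panel does not forbid an INR in someone on warfarin. Section 6.5 says the monitoring should happen, and it does not say that the result must come from the scheduled sample. That reading is possible and it lowers the severity. But no passage states it. Footnote 3 has no exception, and the schedule has no conditional entry, although its other footnotes do carry conditions.

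Appendix 2 also has safeguards. It is a contingency for restricted visits, a telephone assessment decides whether drug may be sent, symptoms can prompt tests, and dispensing pauses after a clinically significant reaction. Section 8.4 separately offers home visits with assessments as per protocol, if staffing permits. All of this stands. None of it says whether the waiver applies to the Section 6.5 groups.

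A reader might infer that a symptom-free rise in creatinine would go unseen by the trial. The documents do not support that for face-to-face visits, because U&E is listed at weeks 12, 24, 36 and 48. A reader might also infer that a participant could complete the whole course before any on-treatment PT. That requires warfarin use, allocation to exenatide, a remote week 12 visit and no INR ordered under Section 6.5. It is a stacked worst case and not what the plan prescribes.

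**Conclusion.** The inconsistency is in the current text and should be corrected, but it is narrow. For INR it arises in the ordinary schedule: PT at 2 of 4 follow-up visits up to week 48, with a nominal 36-week gap. For renal function it arises during treatment only at visits held remotely under Appendix 2. For those visits the INR instruction has the same problem.

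The conclusion assumes that PT is the source of INR and that Section 6.5 applies to trial visits, as it says. INR may be checked in usual care, but the documents do not say so.

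The documents do not give the number of participants on these drugs. The exenatide arm is planned at about 25, and those on warfarin or coumarins are probably few. It would go too far to say that the trial's safety objective fails: that objective rests on adverse event reporting (protocol Section 4; SAP Section 7.8), and laboratory values are not a listed outcome. The sample size, primary endpoint and primary analysis are unaffected.

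**What to change.** Reconcile Section 6.5 with the visit lists in Section 8.4, Appendix 1 footnote 3 and Appendix 2 item 3, so that one INR instruction and one renal instruction apply to participants on the drugs that Section 6.5 lists. Carry the agreed instruction into Appendix 1 as a conditional row or footnote for those participants. State in Appendix 2 whether the blood-test waiver applies to them. The sponsor's clinicians should decide the content of the instruction; this review does not propose one.

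The cost is a protocol wording change. If the clinicians decide to add a test at weeks 24 and 36, blood is already drawn at those face-to-face visits, so it would mean one more test for the few participants concerned. Any sampling during remote visits would cost more, because it would have to be arranged while visits are restricted.
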